4.4.4. Selection of Doses in the Study

Participants will be randomized to one of two arms, as follows:

TOL-463 Vaginal Insert: Administered vaginally as a single 2 g unit dose twice a week with a minimum of a two-day duration in between doses for twelve weeks with the aid of a disposable applicator.

Placebo: Administered vaginally as a single 2 g unit dose twice a week with a minimum of a two-day duration in between doses for twelve weeks with the aid of a disposable applicator.

4.4.5. Selection and Timing of Dose for Each Subject

All subjects will receive TOL-463 Vaginal Insert or placebo administered vaginally as a single 2 g unit dose twice a week with a minimum of a two-day duration in between doses for twelve weeks with the aid of a disposable applicator.

4.4.6. Blinding

Participants, the study staff who dispense study drug and perform study assessments after study drug administration, data entry personnel at the sites, and laboratory personnel will be blinded to treatment assignment. The DSMB may receive efficacy data in aggregate and presented by treatment group, as specified in the DSMB charter. The DSMB may request to be completely unblinded to individual study drug assignments, as needed, to adequately assess SAEs.

Study drug will be prepared at Fisher BioServices in blinded numbered kits. All kits will look identical and contain an identical number of inserts. Emmes will provide an unblinded list identifying the treatment identity (TOL-463 or placebo) in each kit to the Fisher staff responsible for preparing study drug kits. Clinicians, investigators, and all blinded staff will not have access to this list until after the trial has ended.

4.4.7. Prior and Concomitant Therapy

Administration of any medications, therapies, or vaccines will be recorded on the appropriate DCF. Concomitant medications will include all medications taken 30 days prior to the initial screening visit V0, through V4 or early termination, whichever occurs first. Prescription and over-the-counter drugs will be included, as well as herbs, vitamins, and supplements.

Participants who have received study IP and are subsequently diagnosed with a concomitant infection that requires systemic antibiotics will receive treatment according to the local clinic's standard protocols but will

be excluded from per-protocol analyses and terminated from the study. However, participants who have received study IP and are subsequently diagnosed with VVC can remain in the study and be considered evaluable for efficacy if they are appropriate candidates for oral fluconazole therapy.

At the discretion of the site PI, use of new medication should prompt evaluation for the presence of a new diagnosis of chronic medical disease or condition.

Medications that might interfere with the evaluation of the IP should not be used unless absolutely necessary.

4.4.8. Treatment Compliance

The TOL-463 Insert and placebo are inserted by the study participant.

At each follow up visit, V2 through V4, participants will be asked to bring the study IP packaging, unused inserts (if any) and memory aid corresponding to the return visit (V2, V3 or V4) to the study personnel. Study personnel will review adherence to the study IP schedule with the participants, including the participant memory aid, and record this on the appropriate DCF at each follow-up visit and any unscheduled visits. Study personnel will record the number of unused inserts and empty packaging returned at each of the follow-up visits, V2 thru V4. Compliance with the study protocol will be assessed and documented by study personnel at each of the follow-up visits, V2 thru V4, and at any unscheduled visits. Study personnel may discard the participant's memory aid after documenting compliance.

The protocol defines that a participant is compliant with the study treatment if she misses ≤ 2 non-consecutive doses of IP per month, as assessed by participant memory aid and returned IP and packaging at each follow up visit (V2, V3, V4).

A blinded case review committee will review subjects' data to determine if they were compliant with the study treatment throughout the study, for cases that could not be determined programmatically. Subjects will be further excluded from per-protocol population analyses if they were not compliant with the study treatment throughout the study, see section [6.3](#) .

4.5. Efficacy (Immunogenicity) and Safety Variables

Multiple observations within specific visit period are acceptable. In the case of multiple observations within a specific window, the assessment value that is closest to the scheduled visit window will be used in the analyses for the post-baseline records. Whether to use and how to use the observations from early termination at an unscheduled visit along with the observations obtained at the corresponding scheduled visit will be specified in the applicable tables. For screening and baseline visits, the last assessment value will be used. All the recorded data will be listed. If observations have the same distance to the scheduled assessment, the latest one will be used.

4.5.1. Efficacy variables

The primary efficacy analysis estimates the clinical efficacy rate of TOL-463. At each follow-up visit, the Amsel criteria will be assessed, see definition in section [3.3](#) .

For the primary analysis, a participant is deemed to experience a recurrence of BV at a follow-up visit if >2 of the Amsel criteria are met or diagnosed of BV recurrence off site. A participant has clinical suppression of BV if she meets ≤ 2 of the criteria at each observed follow-up visit through V4. See below and section [6.5](#) for handling missing BV status by TOC (visit 4).

The proportion of participants with recurrence of BV (treatment failure) up to and including V4 will be summarized overall and by treatment group along with two-sided 95% Wilson CIs. The primary analysis will be performed in the mITT analysis population. Secondary analyses of the primary outcome measure will be performed in the PP analysis population.

For the mITT analysis population, the BV status of subjects whose status cannot be determined by the TOC visit for any reason or those who withdrew or those who dropped out early will be considered ‘treatment failure’ for primary recurrence endpoint. For the PP analysis population, subjects whose BV status cannot be determined by the TOC visit for any reason will be excluded from the analysis. For secondary endpoints, missing values will be further excluded from the mITT and PP populations.

In addition, the rate of recurrence, which considers the amount of observed follow-up time for each participant, will be estimated within each treatment group along with corresponding 95% CIs. We will use a person-time approach as discussed in section 8.1.

Secondary efficacy analyses will be performed in the mITT and PP analysis populations.

For the analysis of Secondary Objective 1, the time to BV recurrence will be estimated by treatment group using Kaplan-Meier estimates. For participants who experience clinically diagnosed BV recurrence in study by V4, the time of BV recurrence will be defined as the midpoint between the earliest time point of a positive BV diagnosis (post-baseline) and the previous observed time-point. Subjects with BV recurrence diagnosed off study will be treated as missing time to BV recurrence and excluded from the analyses for secondary endpoints, as defined above and in Section 6.5. For participants without BV recurrence at or before V4, the BV recurrence endpoint will be coded as censored, with time to recurrence defined as the elapsed time from the first dose of IP, to the earliest of: V4 time-point, the last observed time-point prior to loss to follow-up, or the time-point at which the participant became ineligible for the particular analysis population.

For the analysis of Secondary Objective 2, the proportion of participants experiencing BV symptoms will be estimated overall, by symptom category, and by treatment group.

For the analysis of Secondary Objective 3, responses to the satisfaction questionnaire will be summarized overall and by treatment group. Categorical responses will be summarized using contingency tables.

Descriptions of the analyses to assess the exploratory objective as well as other analyses that will support the primary and secondary efficacy analyses will be provided in Section 8.4.

4.5.2. Safety variables

Safety will be monitored throughout the study by targeted physical and pelvic examination and participant reporting. Safety will be assessed by the frequency and severity of:

1. Serious AEs occurring after randomization and from the time of the IP dose through V4.
2. Non-serious AEs occurring after randomization and from the time of the IP dose through V4.

4.5.2.1. Adverse Events (AEs)

ICH E6 defines an AE as any untoward medical occurrence in a participant or clinical investigation participant administered a pharmaceutical product regardless of its causal relationship to the study treatment. An AE can therefore be any unfavorable and unintended sign (including an abnormal laboratory finding), symptom, or disease temporally associated with the use of medicinal (investigational) product. The

occurrence of an AE may come to the attention of study personnel during study visits and interviews of a study participant presenting for medical care, or upon review by a study monitor.

All AEs not meeting the criteria for “serious adverse events” should be captured on the appropriated CRF. Information to be collected for AEs includes event description, date of onset, clinician’s assessment of severity, relationship to IP (assessed only by those with the training and authority to make a diagnosis, or his/her designee), date of resolution/stabilization of the event. All AEs occurring while on study must be documented appropriately regardless of relationship. All AEs will be followed to adequate resolution.

Any medical condition that is present at the time that the participant is screened will be considered as baseline and not reported as an AE. However, if it deteriorates at any time during the study, it should be recorded as an AE.

All AEs must be graded for severity and relationship to IP.

4.5.2.2. Adverse Events Grading

FDA defines an AE as any untoward medical occurrence associated with the use of a drug in humans, whether or not considered drug-related. All AEs (laboratory and clinical symptoms) will be graded for severity and assessed for relationship to IP (see definitions). AEs characterized as intermittent require documentation of onset and duration of each episode. The start and stop date of each reported AE will be recorded on the appropriate DCF and electronic case report form, (eCRF). Changes in the severity of an AE will be documented to allow an assessment of the duration of the event at each level of intensity.

Severity of Event:

All AEs will be assessed by the clinician using a protocol-defined grading system (refer to protocol Appendix B). For events not included in the protocol-defined grading system, the following guidelines will be used to quantify severity:

- Mild (Grade 1): Events that are usually transient and may require only minimal or no treatment and generally do not interfere with the participant’s daily activities.
- Moderate (Grade 2): Events that are usually alleviated with additional specific therapeutic intervention. The event interferes with usual activities of daily living, causing discomfort but poses no significant or permanent risk of harm to the research participant.
- Severe (Grade 3): Events interrupt usual activities of daily living, or significantly affects clinical status, or may require intensive therapeutic intervention. Severe events are usually incapacitating.

Changes in the severity of an AE should be documented to allow an assessment of the duration of the event at each level of intensity to be performed. AEs characterized as intermittent require documentation of onset and duration of each episode.

4.5.2.3. Relationship to Study Products:

The clinician’s assessment of the AE’s relationship to IP will be done by those with the training and authority to make an assessment, or his/her designee, and the assessment will be part of the documentation process. Whether the AE is related or not, is not a factor in determining what is or is not reported in this trial. If there is any doubt as to whether a clinical observation is an AE, the event should be reported.

In a clinical trial, the study medication must always be suspect. The relationship to study medication will be assessed for AEs using the terms related or not related:

- Related – There is a reasonable possibility that the study product caused the AE. Reasonable possibility means that there is evidence to suggest a causal relationship between the study medication and the AE.
- Not Related – There is not a reasonable possibility that the administration of the study medication caused the event.

4.5.2.4. Serious Adverse Events (SAEs)

An AE or suspected adverse reaction is considered a SAE if, in the view of either the site PI or sponsor, it results in any of the following outcomes:

- Death,
- a life-threatening adverse event*,
- inpatient hospitalization or prolongation of existing hospitalization,
- a persistent or significant incapacity or substantial disruption of the ability to conduct normal life functions, or
- a congenital anomaly/birth defect.
- Important medical events that may not result in death, be life-threatening, or require hospitalizations may be considered serious when, based upon appropriate medical judgment they may jeopardize the participant and may require medical or surgical intervention to prevent one of the outcomes listed in this definition. Examples of such medical events include allergic bronchospasm requiring intensive treatment in an emergency room or at home, blood dyscrasias or convulsions that do not result in inpatient hospitalization, or the development of drug dependency or drug abuse.

* Life-threatening adverse event. An AE is considered “life-threatening” if, in the view of either the site PI or sponsor, its occurrence places the participant at immediate risk of death. It does not include an AE that, had it occurred in a more severe form, might have caused death.

All SAEs will be:

- Assessed for severity and relationship to study product and alternate etiology (if not related to study product) by a licensed study physician or by the Institution as the site PI or Sub Investigator, (SubI).
- Recorded on the appropriate SAE DCF and eCRF.
- Followed through resolution by a licensed study physician.
- Reviewed and evaluated by DMID, an Independent Safety Monitor (ISM) (as deemed necessary), the DSMB (periodic review unless related), and the IRB/IEC.

5. SAMPLE SIZE CONSIDERATIONS

Efficacy analyses will be performed in an evaluable subset of the enrolled population; this subset was used to derive the study's sample size. Assuming a 40% BV recurrence rate among women receiving placebo and a 50% reduction in recurrence among women treated with TOL-463 (i.e. 20% recurrence rate among TOL-463 recipients) and a 1:1 allocation ratio between treatment arms, a sample size of 200 evaluable participants will provide at least 85% power using the Chi-Square Test. Assuming 80% of enrolled participants will be evaluable for the primary analysis, the enrollment target is set to a total of 250 participants to achieve 200 evaluable participants.

The study was closed early due to the uncertain future of the study product's manufacture and availability. It was unrelated to the safety and efficacy of the study product. The power of the actual sample size will be provided in the CSR.

6. GENERAL STATISTICAL CONSIDERATIONS

6.1. General Principles

Tabulations will be used extensively to summarize the data. All continuous variables will be summarized using the following descriptive statistics: n (sample size), mean, standard deviation, median, maximum and minimum. The frequency and percentages (based on the sample size) of observed levels will be reported for all categorical measures. Missing data will be denoted by n and %. Wilson confidence intervals for binomial proportions and difference in binomial proportions will be computed for efficacy variables.

All summary tables will be structured with a column/sub-table for each treatment group (TOL-463 Vaginal Insert, Placebo) and overall (All Subjects), or each site and overall. The total population size relevant to that table/column if applicable, including any missing observations will be displayed in the tables.

Participants will be excluded from Safety Population if it is unknown whether they received at least one dose, so if they had adverse events, those events would not be included in the safety summary tables, but they will be included in the AE listings. Repeat participants are counted once in all TFLs except for the safety analyses, when a participant met safety population criteria in both enrollments, the participant will be counted twice, i.e., each enrollment will be treated distinctly in the safety summary tables.

Data listings will be provided for all data. Note that in the data listings, Subject ID is the unique subject identifier, not the Study ID used on study and dates will not be included, only Study Day.

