### 10.5.1 Analysis Populations

Safety Population: This analysis population includes all randomized participants who received at least one dose of study treatment.

Modified Intent-to-Treat (mITT) Population: This analysis population includes all randomized participants who are evaluable.

The mITT population will be used as the primary efficacy analysis population.

Per-Protocol (PP) Population: This analysis population includes all randomized participants who met all inclusion/exclusion criteria throughout the study, are evaluable (defined below), complied with the assigned IP, and returned to the study site for the TOC visit within the specified window (Visit 4 [Window: Day 85-91]) or were followed up to their diagnosis of recurrent BV.

Evaluable is defined as follows:

- Negative STI tests taken at baseline (*C. trachomatis*, *N. gonorrhoeae*, or *T. vaginalis*);
- For participants 21 years of age or older, documentation of or self-report of a normal or ASCUS HPV negative Pap test prior to screening, or a Pap smear performed at screening/enrollment with normal result

A participant is compliant with the study treatment if she misses  $\leq 2$  non-consecutive doses of IP per month, as assessed by participant memory aid and returned IP and packaging at each follow up visit (V2, V3, V4).

In the unlikely event of an error in randomization or IP administration (i.e., incorrect treatment), participants will be grouped by the treatment they actually received in safety analyses but will be grouped by their intended randomized assignment in efficacy analyses.

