6.3. Analysis Populations

Safety Population: This analysis population includes all randomized participants who received at least one dose of study treatment. Participants with any evidence of dosing according to the memory aid or study IP packaging return will be included in the Safety population.

Modified Intent-to-Treat (mITT) Population: This analysis population includes all randomized participants who are evaluable (see below). If a participant was enrolled more than once, (participants are allowed to be re-enrolled under PI's discretion for scenarios such as, the first enrollment terminated due to the COVID-19 shelter in place order or became ineligible after enrollment.) only the set of data from the most recent enrollment will be included in the mITT population.

The mITT population will be used as the primary efficacy analysis population.

Per-Protocol (PP) Population: This analysis population includes all randomized participants who are evaluable, complied with the assigned IP (see section 4.4.8), and returned to the study site for the TOC visit within the specified window (Visit 4 [Window: Day 85-91]) or were followed up to their diagnosis of recurrent BV. Participants who violated any inclusion/exclusion criterion at any point during the study or engaged in receptive oral, anal, or vaginal sexual intercourse within 24 hours prior to a study visit will be excluded from the PP population. If a participant was enrolled more than once, (participants are allowed to be re-enrolled under PI's discretion for scenarios such as, the first enrollment terminated due to the COVID-19

shelter in place order or became ineligible after enrollment.) only the set of data from the most recent enrollment will be included in the PP population.

In the unlikely event of an error in randomization or IP administration (i.e., incorrect treatment), participants will be grouped by the treatment they actually received in safety analyses but will be grouped by their intended randomized assignment in efficacy analyses.

Evaluable is defined as follows:

- Negative STI tests taken at baseline (*C. trachomatis*, *N. gonorrhoeae*, or *T. vaginalis*);
- For participants 21 years of age or older, documentation of or self-report of a normal or ASCUS HPV negative Pap test prior to screening, or a Pap smear performed at screening/enrollment with normal result

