9.3. Adverse Events

Safety evaluations will be based on the incidence, severity, and type of AEs, SAEs, clinically significant physical and pelvic examination findings. Safety variables will be tabulated and presented for all participants in the safety population, grouped by type of infection and treatment.

AEs and SAEs will be coded by MedDRA® for preferred term and system organ class. The number of SAEs is likely to be small in this study and will be reported by a detailed listing showing the type, MedDRA®

coding, relevant dates (IP administration dates and AE onset and resolution dates), severity, relatedness, and outcome for each event.

Participants will be excluded from Safety Population if it is unknown whether they received at least one dose, so if they had adverse events, those events would not be included in the safety summary tables or figures, but they will be included in the AE listings. A repeat subject will be re-enrolled under a unique Subject ID and be treated as a distinct subject. If a repeat participant met safety population criteria in both enrollments, the participant will be counted twice, i.e., each enrollment will be treated distinctly in the safety summary tables. All adverse events reported will be documented as unsolicited AEs for this study.

The analyses of Secondary Objective 4 will be conducted in the Safety Population.

When calculating the incidence of adverse events (i.e., on a per subject basis), each subject will only be counted once and any repetitions of adverse events within a subject will be ignored; the denominator will be the total safety population size and population within the actual treatment group.

The number of subjects, the proportion of subjects with related AE/SAE, and the 95% Wilson confidence interval for the proportion of subjects who experienced unsolicited AEs/ SAEs related to study product will be presented overall and by treatment group. In addition, the difference in proportions between the TOL-463 Vaginal Insert arm and the Placebo group and 95% Newcomb confidence intervals (based on the Wilson CI for the individual proportions) will be presented. The occurrence of AEs considered product-related following initiation of study treatment and through the final study visit will be presented in [Table 27](#).

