Early Discontinuation from Treatment ^d	x	xx	x	xx	x	xx
Early Termination from Study ^b	x	xx	x	xx	x	xx

^a Received Treatment includes subjects who successfully received at least one dose of study treatment. It is unknown whether subjects received at least one dose if they were terminated early before Visit 2 and a Study Product Dispensing assessment at the early termination visit could not be conducted.

^b Completed Follow-up includes subjects who remained BV suppressed and were followed-up through Visit 4 as well as subjects whose participation ended prior to Visit 4 due to a clinical BV diagnosis. Terminated Early includes subjects who terminated from the study early for reasons other than a clinical BV diagnosis.

^c A blinded case review committee reviewed subjects' data to determine treatment compliance throughout the study for each subject.

^d Subjects who discontinued treatment due to RBV are included.

Table 4: Analysis Populations by Treatment Group

Analysis Populations	Reason Subjects Excluded	TOL-463 Vaginal Insert (N=X)		Placebo (N=X)		All Subjects (N=X)	
		n	%	n	%	%	n
Eligible for Safety Analysis Population	N/A	x	xx	x	xx	x	xx
Excluded from Safety Analysis Population	Any Reason	x	xx	x	xx	x	xx
	Did not receive at least one dose of study product	x	xx	x	xx	x	xx
Eligible for Modified Intent-to-Treat Analysis (mITT) Population	N/A	x	xx	x	xx	x	xx
Excluded from for Modified Intent-to-Treat Analysis (mITT) Population	Any Reason	x	xx	x	xx	x	xx
	Positive NAAT test results at baseline for C. trachomatis, N. gonorrhoeae, or T. vaginalis	x	xx	x	xx	x	xx
	HPV Criterion ^a	x	xx	x	xx	x	xx
Eligible for Per-Protocol (PP) Analysis Population	N/A	x	xx	x	xx	x	xx
Excluded from Per-Protocol (PP) Analysis Population	Any Reason	x	xx	x	xx	x	xx
	Did not meet inclusion/exclusion criteria	x	xx	x	xx	x	xx
	Positive NAAT test results at baseline for C. trachomatis, N. gonorrhoeae, or T. vaginalis	x	xx	x	xx	x	xx
	HPV Criterion ^a	x	xx	x	xx	x	xx
	Was not compliant with study product	x	xx	x	xx	x	xx
	Did not return to study site for the TOC visit within the specified window (Visit 4, Day 85-91)	x	xx	x	xx	x	xx
	Was not followed up to the diagnosis of recurrent BV	x	xx	x	xx	x	xx

Notes: N=Number of all enrolled subjects

^a For participants 21 years of age or older, documentation of or self-report of abnormal, or ASCUS HPV Positive Pap test prior to screening, or Pap smear performed at screening/enrollment with abnormal result.

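### Adverse events in women whose dosing is unknown are left out of every safety summary, and the halting-rule table covers a narrower population than the halting rules

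*SAP*

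**What the plan says.** Protocol 10.5.1 defines the Safety Population by exposure: "This analysis population includes all randomized participants who received at least one dose of study treatment". It does not say what to do when exposure is unknown.

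The SAP fills that gap in four places:

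- SAP 6.1: "Participants will be excluded from Safety Population if it is unknown whether they received at least one dose". If such women had adverse events, "those events would not be included in the safety summary tables, but they will be included in the AE listings".
- SAP 9.3 repeats the rule and extends it to figures: "those events would not be included in the safety summary tables or figures, but they will be included in the AE listings".
- SAP 6.3 limits the group: "Participants with any evidence of dosing according to the memory aid or study IP packaging return will be included in the Safety population".
- The footnote to SAP Table 3 says who is left: "It is unknown whether subjects received at least one dose if they were terminated early before Visit 2". The same footnote sets a second condition, that product use could not be checked when the woman terminated.

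The summaries of related AEs (Table 27), all AEs (Table 28) and culture-confirmed VVC (Table 36) are on the Safety Population, as is the halting-rule summary (Table 39). The listings of non-serious and serious AEs (Tables 34 and 35) are on all enrolled subjects. Table 3 has a separate row, by arm, for women whose receipt of treatment is unknown. Table 4 gives only one reason for exclusion from the Safety Population, namely that no dose was received.

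**The concern.** Product is handed out at Visit 1 for insertion at home, and the first scheduled review of the memory aid and packaging is at Day 29 to 35. A woman can use the product, have a local reaction, report it remotely and never come back. If nothing is returned, the SAP treats her as unexposed.

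Two inconsistencies follow. First, under Protocol 8.1.1.1 an AE is called related only if there is a reasonable possibility that the product caused it. An investigator may therefore judge an AE product-related in a woman whom the analysis counts as not having taken the product. Second, the halting rules in Protocol 8.6 and SAP 6.6 refer to participants without restriction, while the table that reports on them does not.

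At stake are the proportions, confidence intervals and arm differences for secondary endpoints 4 and 5, and the accuracy of the halting-rule table. The listings keep the events but give no denominators and no comparison between arms.

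**Working it through.** **Plan's own figure.** None depends on this rule, so there is nothing to reproduce.

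**Step 1: who is excluded.** Reading SAP 6.1, 6.3 and the Table 3 footnote together, a woman is excluded for unknown dosing only if she (a) terminated before Visit 2, (b) had no product assessment at early termination, and (c) left no memory-aid or packaging evidence of a dose. The group therefore consists only of early terminations.

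**Step 2: effect on an AE proportion.** Let *n* be the women in an arm, *u* those with unknown dosing, *p* the AE risk in women known to be dosed, and *q* the recorded AE risk in the unknown group.

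- Shown under the SAP: *p*
- With the unknown group counted as exposed: [(*n* − *u*)*p* + *uq*] / *n*
- Shift: (*u*/*n*)(*q* − *p*)

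The sign depends on whether *q* is above or below *p*, and the shift is zero when they are equal. The arm difference moves by the shift in the TOL-463 arm minus the shift in the placebo arm.

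Only *n* is in the documents: about 125 per arm planned (Protocol 5, SAP 4.3). The values of *u*, *p* and *q* below are assumptions, with *p* = 10%.

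| *u* of 125 | *q* = 0 | *q* = 10% | *q* = 50% | *q* = 100% |
|---|---|---|---|---|
| 2 | 9.8% | 10.0% | 10.6% | 11.4% |
| 6 | 9.5% | 10.0% | 11.9% | 14.3% |
| 12 | 9.0% | 10.0% | 13.8% | 18.6% |

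Example: *u* = 6, *q* = 50% gives (119 × 0.10 + 6 × 0.50)/125 = 14.9/125 = 11.9%. With *q* = 0 it gives 11.9/125 = 9.5%.

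Across this assumed grid the proportion moves by −1.0 to +8.6 percentage points from the 10% that the SAP would show. SAP 5 says that the study closed early but gives no final enrolment. In a smaller arm each such woman weighs more: with an assumed 60 per arm, one unknown woman with an event gives (59 × 0.10 + 1)/60 = 11.5%.

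**Step 3: Table 39.** This step needs no assumed rate.

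- Halting rule 1 is met by one participant with a related SAE, in any population.
- Table 39 counts the Safety Population and shows the tally out of 1.
- If the only related SAE is in a woman with unknown dosing, the rule is met but the table shows 0 of 1.
- For rule 2, two related Grade 3 AEs, one of them in such a woman, would show as 1 of 2.

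**Step 4: Table 4.** With a single exclusion reason, women with unknown dosing are either filed as not dosed, which is not known, or have no row at all.

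**The case against.** The strongest case is that the rule is narrow, disclosed and faithful to the protocol. Much of it stands.

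- **The events are not lost.** They appear by treatment group in Tables 34 and 35, with severity, relatedness and outcome. Table 3 shows the size of the group by arm, and Listings 2 and 3 give reasons for early termination. This stands.
- **Proof of dosing is not demanded.** Any memory-aid or packaging evidence is enough. This stands, although SAP 6.3 does not name a verbal report as evidence.
- **The feared case may be rare.** AEs and product use are assessed at the same visits, so a recorded AE without a product assessment mostly means contact outside a visit. Many of these women will have no AE data. Protocol 2.3.1.1 also says that no treatment-related AE led to discontinuation of study product in earlier TOL-463 trials. This stands, and it is why *q* could be below *p*.
- **Early termination is not intolerance.** SAP 6.3 mentions COVID-19 orders and women found ineligible after enrolment. This stands.
- **Halting itself is safe.** SAEs go to the sponsor within 24 hours (Protocol 8.3.1) and are reviewed in real time (Protocol 8.7.2). This stands; Table 39 is a report, and only its content is affected.
- **The protocol defines safety by doses received.** Making dispensed product the main definition would depart from it. This stands, and it argues for a sensitivity analysis instead of a new main population.

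None of these points supplies a comparison that includes the excluded events, or makes Table 39 agree with the rules it summarises.

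**Conclusion.** The point holds as one of incomplete safety summaries and a mismatched halting table. Women with unknown dosing are treated as unexposed, and their AEs, related or not, appear only in listings. The effect on AE proportions and arm differences could be in either direction. Its size cannot be computed from the documents, because neither the number of such women nor any AE rate is given, and it is zero if their AE risk equals that of dosed women. The table above shows arithmetic on assumed inputs and is not an estimate. The Table 39 mismatch follows from the text alone.

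A reader might infer that the plan understates harm or hides early intolerance. The documents do not support that: the group may have terminated for reasons unrelated to the product, and its recorded AE risk may be lower than that of dosed women. A reader might also infer that a related SAE could escape the halting process. It could not, since the rules and the SAE reporting apply to every participant.

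This is a cheap improvement, worth making to protect the safety conclusions.

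**What to change.** 1. Keep the protocol-defined Safety Population for the main safety analysis.
2. Repeat Tables 27, 28 and 36 as a sensitivity analysis in all randomised women to whom product was dispensed, except those shown by memory aid or returned packaging to have taken no dose. Amend the denominator notes of Tables 27 and 36 for this version, since they refer to women who used at least one insert.
3. Base Table 39 on all enrolled subjects, so that it matches the halting rules. The rules themselves need no change.
4. Add an unknown-dosing row to the Safety Population exclusions in Table 4.

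The cost is some SAP wording and a few extra or amended tables, on data already collected. The downside is that the sensitivity version may include women who never took a dose or who have no AE follow-up, which would dilute the rates. That is why both versions should be shown side by side.
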